3.4.9 Data Collection Instruments – The Data Collection Package

The following variables will be collected for participants in both arms of the trial, as well as the registry. This information will be obtained from existing electronic databases as well as hospital charts.

1. Patient Demographics/Hospital Length of Stay
2. Preoperative Cardiac Information
3. Preoperative Comorbidities
4. Lab Results (pre and post-op)
5. Echocardiogram Information
6. Angiogram Information
7. Procedure Information

8. Medications (pre and post-op)
9. Post-Operative Delirium
10. Post-Operative Complications
11. 30 Day Readmission
12. 12 Month Readmission

3.5 Study Protocol

3.5.1 Screening implementation Plan

Following training, clinicians will complete a *CFS* score for every new cardiac surgery consult at each of the participating sites. Patients with a *CFS* ≥ 3 will be eligible for enrolment and notification will be sent to the site coordinator. Patients who are eligible for the study (*CFS* ≥ 3) will either be consented in person or via telephone consent process. Patients with a *CFS* ≥ 3 that either refuse to be randomized or are deemed “unsafe” will be given the opportunity to enroll in a follow up registry.

3.5.2 Safety and Baseline Assessments

A medical director, at each site, will oversee all cases and ensure patient eligibility and safety for program initiation and throughout program attendance for the study duration. All eligible and consented patients will be evaluated at baseline to ensure angina stability. Exercise prescription will be determined utilizing the standard practice of the Karvonen Equation adjusted according to pre-program exercise stress test. (21)Patients will also undergo a standard *6MWT* (73)(74)(75)(76)(77)(78) and will repeat the *6MWT* at the preoperative time point in both the control and *Prehab* groups to determine impact of the intervention. The *6MWT* was chosen because it requires minimal infrastructure and personnel to complete and has been demonstrated to be a valid prognostic tool for patient outcomes and is comparable to an exercise-stress test. (73)(75)(76)(77)This approach enables us to avoid potential scheduling issues that occur if a patient’s surgical date is moved up.

Patients who are deemed appropriate for enrolment into study will be randomized, following the completion of the baseline data collection, to one of two trial arms – control (standard of care (*StandC*) or treatment (*Prehab*). Baseline risk factor evaluation, anthropometrics, clinical markers, patient questionnaires (including frailty scores, cognitive assessment, and quality of life data) and physical activity data measured using accelerometers will be collected for all patients and repeated pre-operatively and at three-month follow up. Safety data including new hospitalization, worsening angina or heart failure and arrhythmias will be captured and all adverse events will be reportable to the study Data Safety Monitoring Board (*DSMB*). All patients in both groups will be referred to postoperative *CR* programming, as per local practice.

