5.1.2 Secondary Outcomes

(1) pre-operative frailty, (2) exercise capacity, (3) physical activity behavior, (4) in-hospital outcomes, (5) 1-year clinical outcomes, (6) 1-year health-related quality of life, (7) cost-analysis.

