5.2 Statistical/Analytical Plan

Objective 1: To determine if *Prehab* reduces the proportion of frail elderly patients requiring a prolonged hospital length of stay of >7 days. A univariable analysis will be undertaken to determine if hospital *LOS* > 7 days is associated with frailty and other patient-level factors. A stepwise multivariable logistic regression model will then be developed to determine if *Prehab* attendance is independently associated with a decreased risk of prolonged hospital length of stay > 7 days. As a secondary analysis, hospital *LOS* will also be compared as a continuous variable between the *Prehab* and standard care groups using a Mann-Whitney test.

“The PREHAB Study” (Pre-operative Rehabilitation for reduction of Hospitalization After coronary Bypass and valvular surgery.)

Objective 2: Does attending *Prehab* influence frailty, exercise capacity, physical activity behavior, in-hospital complications, and *HRQoL*? Although we will employ four different measures of frailty, based on our preliminary data and based on a Task Force’s position statement(90), the Modified Fried Criteria will be the primary frailty outcome over time from baseline to the end of *Prehab* program (pre-operatively), or from baseline to the 3-month post-operative follow-up. The primary measure of exercise capacity will be the *6MWT* and will be analysed with univariable linear regression models to evaluate the association between the *6MWT* and *Prehab* attendance. Accelerometers will be used to objectively measure the number of minutes spent performing moderate to vigorous physical activity (*MVPA*) and total physical activity (*TPA*) per day for a period of 7 days and compared between groups. A composite outcome for a major adverse cardiac event (i.e. *MACCE* = in-hospital stroke, myocardial infarction, renal failure requiring dialysis and death) and delirium will be compared between groups using a Chi-Square or Fisher’s Exact test. A multivariable logistic regression will be used to identify if *Prehab* is independently associated with in-hospital delirium. The *SF-12v2* and *EQ-5D* scores, after normative standardization, will be analyzed through use of a repeated *ANOVA* to allow for a standardized group and group/time interaction effect estimation.

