5.3 Sample Size Calculation

The sample size calculation was based on the primary objective – determining the effect of *Prehab* on rates of prolonged hospital length of stay > 7 days. Our preliminary data, demonstrated the proportion of frail patients in the Control group with a hospital length of stay > 7 days to be 58.3%. For the *Prehab* group, based on improvements in functional capacity in our pilot *RCT* and the work by Arthur et al14, we believe an absolute 20% reduction in proportion of patients that require prolonged hospital length of stay of greater than 7 days, is feasible. A sample size of 194 individuals (97 in each group) will be required for a two-tailed test at an alpha of 0.05 and power of 80%. All patients assigned to the pilot *Prehab* group completed the intervention, however, we are mindful that we will be recruiting frail, elderly patients who may have a higher dropout rate. Hence, we are estimating a 20% dropout rate and plan to recruit 244 individuals (122 in each study arm) to achieve an eventual sample size of 194 after dropout.

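### Section 5.2 gives the pre-randomization accelerometer recording no stated role in the physical-activity comparison; adjusting for it would cost nothing and can only help precision

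*Combined protocol and SAP*

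**What the plan says.** Section 3.5.2 states that "physical activity data measured using accelerometers will be collected for all patients and repeated pre-operatively and at three-month follow up". The same section says that patients "will be randomized, following the completion of the baseline data collection", so the first recording precedes allocation in both arms and is a legitimate covariate.

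Section 5.1.2 lists the outcome as item "3) physical activity behavior", and it is also part of research question ii in section 2.4.

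The whole analysis statement is one sentence in section 5.2, Objective 2: MVPA and TPA minutes are taken "per day for a period of 7 days and compared between groups". It names no test, model, follow-up time point, change score or covariate.

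The same paragraph does bring in baseline or time for other outcomes. The modified Fried criteria "will be the primary frailty outcome over time from baseline to the end of" the program or to 3 months, and the quality-of-life scores get a repeated-measures ANOVA "to allow for a standardized group and group/time interaction effect estimation". Section 3.5.5.6 mentions accelerometers again, but only to check self-reported against measured activity in the Prehab arm.

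**The concern.** A pre-randomization measurement of the outcome is planned in every patient, and the analysis text does not say what it is for. If the comparison is run on follow-up values alone, between-patient variation that baseline could explain stays in the error term. The estimate also carries whatever baseline difference chance produces.

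Because the choice is open, it could also be made after the data are seen. Follow-up-only, change-from-baseline and baseline-adjusted analyses can give noticeably different point estimates in a single trial.

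**Working it through.** **1. The plan's own figure.** The documents state no SD, effect size or power for the accelerometer outcome. The only calculation is for the primary outcome (section 5.3): 58.3% against 38.3%, two-sided 0.05, 80% power.

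- Pooled-variance formula without continuity correction: n per arm = [1.96·√(2·0.483·0.517) + 0.842·√(0.583·0.417 + 0.383·0.617)]² / 0.20² = 96.8, so 97 per arm and 194 in all.
- Dropout: 97/0.8 = 121.25, so 122 per arm and 244 in all.

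Both match the plan, and this point does not touch them. I use 97 per arm below as the evaluable number for the accelerometer comparison. That is an assumption; missing recordings would lower it.

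**2. Precision.** With equal variances and baseline/follow-up correlation r, the variance of the arm difference relative to follow-up only is 1 − r² with baseline as covariate and 2(1 − r) for a change score. At 97 per arm, follow-up only has 80% power for a difference of (1.96 + 0.842)·√(2/97) = 0.402 SD. Power after adjustment for that same difference is Φ(2.80/√(1 − r²) − 1.96).

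| r (assumed) | Variance factor | Detectable difference, 80% power | Power for 0.402 SD, adjusted | Power for 0.402 SD, change score |
|---|---|---|---|---|
| 0 | 1.00 | 0.402 SD | 80% | 50.8% |
| 0.3 | 0.91 | 0.384 SD | 83.6% | 65.8% |
| 0.5 | 0.75 | 0.348 SD | 89.9% | 80.0% |
| 0.7 | 0.51 | 0.287 SD | 97.5% | 95.1% |

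At r = 0.5 the adjusted analysis is worth about 97/0.75 = 129 per arm unadjusted. Adjustment is never worse than either alternative, apart from one degree of freedom. A change score is worse than follow-up only whenever r < 0.5.

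**3. Chance imbalance.** The baseline mean difference has standard error √(2/97) = 0.144 SD, so differences up to 1.96 × 0.144 = 0.28 SD lie within the 95% range. At a 0.28 SD imbalance, the unadjusted estimate shifts by r × 0.28, which is 0.08, 0.14 or 0.20 SD for r = 0.3, 0.5 or 0.7. The two-sided type I error conditional on that imbalance is 7.9%, 12.9% or 20.5%. Averaged over all randomizations it remains 5%.

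**4. What the pilot can say about r.** The protocol's accelerometry table (the first Table 9) labels its ± values as standard errors; Table 3 of the appended pilot manuscript labels the same numbers as SDs. Only the first reading fits the printed confidence intervals: read as SDs, the implied correlations fall below −1.

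Read as standard errors, with 6 and 7 patients and t = 2.201 on 11 df, MVPA in 10-minute bouts gives:

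- Standard error of the change difference: (291 + 135)/2/2.201 = 96.8 min/week.
- Standard error of the follow-up-only difference: √(51² + 53²) = 73.6 min/week.
- Pooled SDs: baseline 100.2, follow-up 133.5, change 173.9.
- Implied r: (100.2² + 133.5² − 173.9²)/(2·100.2·133.5) = −0.09.

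The same steps give 0.28 for sporadic MVPA and −0.31 for sporadic total activity. Total activity in 10-minute bouts gives 0.64, but that rests on an implausible printed baseline of 23 ± 150. With 13 patients none of these fixes r, so the range above starts at 0.

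**5. What the pilot can say about imbalance.** Baseline MVPA in 10-minute bouts was 21 (Prehab) against 82 (standard care) min/week, a gap of −61. This shows that imbalance occurs in very small arms. It does not measure the gain from adjustment at 97 per arm.

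**The case against.** The strongest reply is that section 5.2 is silent rather than wrong. A reader might infer that the plan commits to a follow-up-only comparison and discards baseline. The text does not say so, and the team's own precedent points the other way: the pilot used a two-way ANOVA with time as a repeated factor and reported postoperative-minus-baseline differences. That part of the reply stands, so the supportable statement is that baseline has no stated role. It does not settle the matter, because the precedent is not carried into section 5.2. With baseline and one follow-up, the pilot's group-by-time contrast is also a change score, which is the weaker method when r is low.

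A reader might also infer from the pilot that follow-up activity mostly reflects who was active at the start, or that the choice of analysis reverses the result. For total activity in 10-minute bouts the difference is 193 − 198 = −5 at follow-up and +75 as change; for MVPA it is 147 − 130 = +17 and +78. The documents do not support either inference. For all four measures the standard error of the change difference exceeds that of the follow-up-only difference (97 v 74, 134 v 110, 107 v 89, 277 v 214 min/week), the opposite of what strong tracking would produce. The +78 and +75 are change scores with very wide intervals (−135 to 291 and −221 to 370), not what baseline adjustment would give. For MVPA the implied slope is −0.09 × 133.5/100.2 = −0.12, so the adjusted difference would be about 17 − (−0.12 × −61) = +10, close to the follow-up-only value.

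Finally, this is one of seven secondary outcomes and the unadjusted randomized comparison is valid. Both are true, and they limit the importance of the point. They are not a reason to leave the model unnamed when the better one needs no extra data.

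**Conclusion.** The point holds as a free improvement to a secondary analysis. The baseline accelerometer recording is planned in every patient before randomization and has no stated use in the between-group comparison. Using it as a covariate reduces variance by 0% at r = 0, 25% at r = 0.5 and 49% at r = 0.7. Power of 80% on follow-up values alone becomes 80%, about 90% and 97.5% respectively. It also removes the conditional distortion from chance imbalance.

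These sizes rest on an assumed correlation, equal variances and 97 evaluable recordings per arm, none of which the documents supply for this outcome. The lower end of the range is a real possibility. The unadjusted analysis is not biased on average, its unconditional type I error is 5%, and neither the primary outcome nor the sample size of 194 evaluable and 244 recruited is affected.

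**What to change.** In section 5.2, replace the between-group phrase for MVPA and TPA with wording to this effect: follow-up minutes per day will be analysed by linear regression on assigned arm, with the same patient's pre-randomization minutes per day as covariate, separately for the pre-operative and 3-month recordings; the adjusted difference and its 95% confidence interval will be reported; minutes will be transformed if skewed.

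Add which of the two recordings is the main one, and how missing recordings are handled. The choice needs care: the appended pilot manuscript reports that 11 of 15 participants had surgery within 1–3 days of notification, less than the minimum wear time of 4 days, so the pilot could not analyse its pre-operative recordings.

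The cost is two or three sentences in section 5.2, fixed before the data are examined by arm. No new measurements, visits or patients are needed.

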3.5.3 Randomization

Trial Randomization using *REDCap*: The Randomization Module within *REDCap* allows researchers to randomly assign participants to specific groups. [name] has experience and will be responsible for study randomization. Assessors of pre- and post-operative data will be blinded to treatment group allocation.(47)

3.5.4 Standard care

Patients in the *StandC* group will receive care as is currently delivered to patients awaiting cardiac surgery at each site. At present, patients are advised to rest and participate in very light intensity physical activity while awaiting surgery. At 1-2 weeks prior to their scheduled surgical date, the patient attends a single three hour cardiac pre-assessment with a nurse practitioner and cardiac anesthesiologist. In addition, a cardiac nurse counsels each patient on healthy behaviors (e.g. smoking cessation, diet, exercise).

“The PREHAB Study” (Pre-operative Rehabilitation for reduction of Hospitalization After coronary Bypass and valvular surgery.)

3.5.5 Prehab Intervention

Patients in the *Prehab* group will receive, in addition to the above standard of care, an eight-week comprehensive exercise therapy and education program at a community-based *CR* facility. This program will target both the physical and psycho-social-cognitive aspects of cardiac disease and frailty. In brief, participants will be required to complete an intake health status assessment by the *CR* team including a physiotherapist, cardiovascular nurse, and dietitian and complete a symptom-limited graded exercise stress test according to the American College of Sports Medicine Guidelines for Exercise Testing and Prescription 7th Edition.(79) Patients will be asked to complete at least two sessions of supervised, structured exercise class plus have the option to attend one additional exercise class per week for eight-weeks, with progression to a moderate to high-intensity interval program based on the supervised assessment of the patient’s capabilities. This has been shown to be safe and effective in unrepaird heart failure and elderly patients.(7)(8)(9)(14)(16)(80)(81) *Prehab* participants will also attend four education sessions on topics such as risk factor reduction, medication use, cardiovascular physiology, smoking cessation, healthy eating, exercise, and stress management and promotion of self-managed care.(82)(83)(84) Principles of shared decision-making will be utilized with the *Prehab* intervention, where training for providers and patients involved in the intervention will have shared control of treatment decisions.(82)(83)(84)

Participants in the intervention group will receive a baseline health assessment at their local cardiac rehabilitation facility. This assessment will include the facility’s standard health and fitness assessment: health screening, blood pressure, lung function, lab work, and body composition. This assessment will provide the basis for an individualized exercise prescription, to include an 8 week, individualized, symptom limited, exercise program.

Briefly, patients will be required to attend a minimum of 2 structured exercise sessions per week. The program will last a total of 8 weeks, or until the patient undergoes their cardiac procedure (minimum of 4 weeks for data collection purposes). Patients will be encouraged to walk daily in addition to attending the scheduled exercise sessions. Exercise will be prescribed according to standardized procedures at the medical fitness facility for their cardiac rehabilitation program. Briefly, participants will complete a warm-up/stretching session of approximately 15 minutes at the beginning of each session. Aerobic exercise will be prescribed at 40-60% of heart rate reserve (Karvonen Formula) based on baseline exercise stress test data. Aerobic exercise will last approximately 10-30 minutes depending on individual tolerance and level of conditioning. Aerobic prescription will progress to high intensity exercise in the context of symptom-limited, interval training up to 85% of maximal aerobic capacity based upon recommendations by the cardiologist. Individual interest will determine the modality of exercise chosen. Options will include walking, cycling, stretching and resistance training with body weight or resistance bands following clearance by a cardiologist. Intensity will be progressed based on close communication between healthcare providers and participants. Sessions will be concluded with a 10-minute cool down period.

In addition to the exercise program, patients will be required to participate in 4 educational sessions tailored to self-management for cardiac rehabilitation. Examples of educational sessions offered by professional staff at the medical fitness facility include:

- Exercise and Action Planning (Kinesiologist)
- Risk Factor Modification (Nurse/Physiotherapist)
- Cardiac Electrical System (Nurse/Physiotherapist)
- Cardiac Circulation (Nurse/Physiotherapist)
- Cardiac Muscle Function (Nurse/Physiotherapist)
- Resistance Training (Kinesiologist)
- Body-Mind Connection (Social Worker)

“The PREHAB Study” (Pre-operative Rehabilitation for reduction of Hospitalization After coronary Bypass and valvular surgery.)

Heart Healthy Eating (Dietician)
Looking Forward; transitions, barriers, self-management (Kinesiologist)
Diabetes Education (Dietician)
Emotional Impact of Heart Disease (Social Worker)
Label Reading (Dietician)
Preventing Relapse (Social Work)
Stress Busters (Psychologist)
Tracking Food Choices (Dietician)
Smoking Cessation (Social Worker)
Relaxation Techniques (Psychologist)

Participants in the intervention group will be asked to keep a log of their attendance at both the exercise and educational session. Additionally, an exercise log completed by individual patients will track the mode of exercise completed in addition to monitoring compliance with the intervention.

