3.5.5.6 Exercise training and leisure time activities

After the baseline assessments described above are completed, the *PREHAB* patient will engage in the 8-week *PREHAB CR* exercise therapy program. The first four weeks of the program constitutes a more structured program, the *CR* Centre staff closely monitor the patient during their exercise program and follows their progress. The patient attends the *CR* Centre for two 1 hour sessions of exercise training for the first four weeks. Exercise intensity is typically prescribed at 85% of their maximum heart rate-reserve, unless advised otherwise by the Internist. The remaining 4 weeks is less-structured and the patient is given more autonomy on the manner in which they complete their exercise therapy program. The patient engages in an individually prescribed exercise program consisting of aerobic, strength, and flexibility training. Frequency, time, and type of exercise varies depending on what the patient chooses. The majority of aerobic exercises consist of walking, cycling, rowing, and many machine-based aerobic

“The PREHAB Study” (Pre-operative Rehabilitation for reduction of Hospitalization After coronary Bypass and valvular surgery.)

exercises. A Strength and Stretch class is also offered to increase muscle strength and endurance, and flexibility.

In addition to participating in physical activity at the *CR* Centre, patients are encouraged to participate in physical activities during their leisure time. This includes, but is not limited to, walking outdoors, gardening, household chores, grocery shopping, and cycling. This component of the *CR* program is designed to help patients manage their cardiac disease after they complete *CR*. Patients will be assigned an accelerometer to wear to be able to compare self-assessed exercise reporting with objective measurements.

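### Sections 3.5.5 and 3.5.5.6 give inconsistent aerobic intensity rules for the Prehab arm: the usual intensity, the scale of the 85% figure and the physician role all differ

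*Combined protocol and SAP*

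**What the plan says.** Section 3.5.5 (Prehab Intervention) sets the aerobic dose: "Aerobic exercise will be prescribed at 40-60% of heart rate reserve (Karvonen Formula) based on baseline exercise stress test data". High intensity comes later, as symptom-limited "interval training up to 85% of maximal aerobic capacity based upon recommendations by the cardiologist". The same section adds that intensity moves up through close communication between providers and participants. Its general description of the programme, like the synopsis, also speaks of graded exercise, "with progression to a moderate to high-intensity interval program based on the supervised assessment" of what the patient can do.

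Section 3.5.5.6 (Exercise training and leisure time activities) describes the same eight-week programme. It opens on timing: "The first four weeks of the program constitutes a more structured program". After giving the sessions for those weeks, and before turning to the remaining four, it says: "Exercise intensity is typically prescribed at 85% of their maximum heart rate-reserve, unless advised otherwise by the Internist".

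Two other statements bear on the dose without fixing a percentage. Section 3.5.2: "Exercise prescription will be determined utilizing the standard practice of the Karvonen Equation adjusted according to pre-program exercise stress test". Section 3.5.5: "Exercise will be prescribed according to standardized procedures at the medical fitness facility for their cardiac rehabilitation program".

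**The concern.** Both sections describe one intervention arm, and both are current text. A rehabilitation centre that takes its exercise rule from 3.5.5 begins in a moderate band and progresses. A centre that takes it from 3.5.5.6 finds 85% given as the usual prescription, on a different scale, with a different physician named.

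The point has practical weight for two reasons. Delivery is spread over five sites, each partnered with one or more community rehabilitation centres (section 3.2), so many people outside the coordinating centre will read the exercise text. The patients are aged 60 or older with a Clinical Frailty Score of at least 3 and below 7, and may have moderate aortic or mitral stenosis (section 3.3.1). For them, intensity is a clinical safety setting as well as a description of the treatment. A trial that hopes to see its programme adopted also needs to state the exercise dose once.

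**Working it through.** No figure stated in the plan is in dispute, so the main check is a comparison of text.

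| Element | Section 3.5.5 | Section 3.5.5.6 |
|---|---|---|
| Usual intensity | 40-60% of heart-rate reserve, then progression | typically 85%, no lower level given |
| Scale of the 85% | maximal aerobic capacity | heart-rate reserve |
| Role of the 85% | ceiling for symptom-limited intervals | typical prescription |
| Physician | cardiologist, whose recommendations inform progression | Internist, who may advise otherwise |
| Timing | progression over the programme | stated within the text on the first four weeks |

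**Does another section settle it?**
- Section 3.5.2 names the Karvonen method and the stress test but gives no range.
- The reference in 3.5.5 to facility procedures does not hand the choice to the centre, because the same paragraph fixes 40-60%.
- Section 3.5.5.4.2 says that the stress test informs the prescription but gives no percentage.
- Section 3.5.6 (Variable Waitlist Time) places the more intensive exercise therapy in the first four weeks but gives no intensity.
- The appended pilot report used 85% of maximal oxygen consumption. That was a completed study of bypass patients only, so it does not set the rule here.

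**Size, if 3.5.5.6 is the initial dose.** Both sections use heart-rate reserve, so the gap can be taken directly: 85 − 60 = 25 percentage points above the top of the 3.5.5 band.

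In beats per minute the documents give no inputs, so the resting and peak rates below are assumptions. Karvonen target = rest + f × (peak − rest), with f = 0.40, 0.60 and 0.85:
- rest 60, peak 110: 80 to 90 against 102.5, a gap of 0.25 × 50 = 12.5
- rest 70, peak 130: 94 to 106 against 121, a gap of 0.25 × 60 = 15
- rest 70, peak 150: 102 to 118 against 138, a gap of 0.25 × 80 = 20
- rest 60, peak 150: 96 to 114 against 136.5, a gap of 0.25 × 90 = 22.5

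The gap above the top of the band is thus about 12 to 23 beats per minute over this assumed range.

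**Size, if 3.5.5.6 is the progressed target.** The comparator is then the 85% ceiling in 3.5.5. There is no gap in the nominal figure; the scale and the physician role still conflict.

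**Sample size.** Exercise intensity is not an input to section 5.3. With 58.3% against 38.3%, two-sided alpha 0.05 and 80% power, the pooled formula without continuity correction is n = [1.96 × √(2 × 0.483 × 0.517) + 0.842 × √(0.583 × 0.417 + 0.383 × 0.617)]² / 0.20² = 96.8, so 97 per arm. Then 97 / 0.8 = 121.25, so 122 per arm. The stated 194 and 244 reproduce and do not depend on this point.

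**The case against.** The strongest case for leaving the text alone is that 3.5.5 gives the rule and 3.5.5.6 only describes what centres usually do. The first is written as an instruction and the second in the descriptive present, softened by *typically*. Section 3.5.5.6 never says that patients start at 85%; that reading rests on where the sentence sits. This stands, and it is why the 25-point gap is conditional. It does not remove the conflict, because the document never says which section governs, and the scale and the physician role differ on either reading.

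The second argument is that the percentages do not operate unsupervised. This also stands. Section 3.3.2 excludes severe stenosis, dynamic outflow obstruction, NYHA IV or CCS IV symptoms, critical left main disease and exercise-induced ventricular arrhythmia. Section 3.5.5.4.2 requires a stress test supervised by a physician. Under section 3.5.2, "A medical director, at each site, will oversee all cases", and section 3.5.5.2 adds a medical advisor and an emergency plan. Section 4 requires stability checks twice a week. These safeguards limit the risk, but they do not tell a centre which intensity rule applies.

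A reader might infer a sharper contrast: that 3.5.5 withholds high intensity until the cardiologist approves it, while 3.5.5.6 grants it until the Internist objects. The text does not support that. Section 3.5.5 treats progression as the planned course, and it also relies on provider-participant communication and supervised assessment, so the cardiologist is not a sole gatekeeper.

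**Conclusion.** The inconsistency is real and minor. Sections 3.5.5 and 3.5.5.6 differ for the same arm in usual intensity, in the scale of the 85% and in the physician named, and no other section resolves this. The size depends on the reading: 25 points of heart-rate reserve above the top of the 3.5.5 band if 3.5.5.6 gives the initial dose, or a conflict of scale and physician role alone if it gives the progressed target. The documents do not decide between these.

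Two further inferences go too far. It is not shown that centres will in fact treat similar patients differently, since prescriptions are individualised and medically overseen. Nor does the point threaten the inference: the randomised comparison, sample size, alpha and power are unaffected.

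**What to change.** Replace the intensity sentence in 3.5.5.6 with a cross-reference to the 3.5.5 rule: 40-60% of heart-rate reserve, then symptom-limited progression up to the 85% ceiling. In both sections, express the ceiling on one scale and name one physician role. The clinical leads should choose both. Keeping maximal aerobic capacity leaves the 3.5.5 ceiling as it is, whereas moving to heart-rate reserve changes it and should be a deliberate decision. The new text should not make progression conditional solely on that physician's recommendation, because 3.5.5 contains no such restriction.

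The cost is one replaced sentence, a matching edit for scale and role, and a notice to the rehabilitation centres. The downside is that a centre now using 85% from the outset would move to graded progression, leaving less high-intensity time for patients with only a four-week wait.
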